#### **Safety/reactogenicity**

- For a given subject and the analysis of solicited AEs, four days post-vaccination (Day 0-Day 3), missing or non-evaluable measurements will not be replaced. Therefore the analysis of the solicited AEs based on the TVC will include only vaccinated subjects and doses with documented safety data (i.e., symptom screen completed).
- For a given subject, missing neurodevelopmental status will not be replaced. Therefore, an analysis will exclude subjects with missing or non-evaluable measurements
- For analysis of unsolicited AEs, such as SAEs or AEs by primary Medical Dictionary for Regulatory Activities (MedDRA) term, and for the analysis of concomitant medications, all vaccinated subjects will be considered. Subjects, whose parent(s)/LAR(s) do not report the event or the concomitant medication, will be considered as subjects without the event or the concomitant medication, respectively.
- For summaries reporting both solicited and unsolicited AEs, all vaccinated subjects

will be considered. Subjects, whose parent(s)/LAR(s) do not report the event or the concomitant medication, will be considered as subjects without the event or the concomitant medication, respectively.

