5.4. Analysis of safety and reactogenicity

5.4.1. Analysis of safety and reactogenicity planned in the protocol

The primary analysis will be based on the TVC. If more than 5% of enrolled subjects are excluded from the ATP cohort for analysis of safety, then a second analysis based on this ATP cohort will be performed to complement the TVC analysis. All analyses will be descriptive.

- The percentage of subjects with at least one local symptom (solicited or unsolicited), with at least one general symptom (solicited or unsolicited) and with any symptom (solicited or unsolicited) during the 4-day (Day 0-Day 3) solicited follow-up period will be tabulated with exact 95% CI [Clopper, 1934]. The same calculations will be done for symptoms (solicited or unsolicited) rated as grade 3 in intensity, for symptoms (solicited or unsolicited) leading to medical advice and for symptoms (solicited or unsolicited) assessed as causally related to vaccination.
- The incidence of local AEs (solicited and unsolicited) will be calculated at each injection site as well as overall (all sites considered) for each group.
- The percentage of subjects reporting each individual solicited local and general symptom during the 4-day (Day 0-Day 3) solicited follow-up period will be tabulated after the vaccine dose, with exact 95% CI [Clopper, 1934]. The same calculations will be done for each individual solicited symptom rated as grade 3 in intensity and for each individual solicited symptom assessed as causally related to vaccination.
- All computations mentioned above will be done for Grade ≥ 2 (solicited symptoms only) and grade 3 symptoms, for symptoms considered related to vaccination (general symptoms only), for grade 3 symptoms considered related to vaccination (general symptoms only) and for symptoms that resulted in a medically-attended visit.
- Occurrence of fever and related fever will be reported per 0.5°C cumulative temperature increments as well as the occurrence of grade 3 fever ($> 39.0^{\circ}\text{C}$ axillary temperature) with causal relationship to vaccination.

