- For a given subject and the analysis of solicited AEs, four days post-vaccination (Day 0-Day 3), missing or non-evaluable measurements will not be replaced. Therefore, the analysis of the solicited AEs based on the TVC will include only vaccinated subjects and doses with documented safety data (i.e., symptom screen completed).
- For a given subject, missing neurodevelopmental status will not be replaced. Therefore, an analysis will exclude subjects with missing or non-evaluable measurements

- For analysis of unsolicited AEs, such as SAEs or AEs by primary Medical Dictionary for Regulatory Activities (MedDRA) term, and for the analysis of concomitant medications, all vaccinated subjects will be considered. Subjects, whose parent(s)/LAR(s) do not report the event or the concomitant medication, will be considered as subjects without the event or the concomitant medication, respectively.
- For summaries reporting both solicited and unsolicited AEs, all vaccinated subjects will be considered. Subjects, whose parent(s)/LAR(s) do not report the event or the concomitant medication, will be considered as subjects without the event or the concomitant medication, respectively.

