Compliance % = (number of doses with symptom sheet return / number of administered doses) X 100

Template 17 Percentage and nature of <grade 3>symptoms (solicited and unsolicited) reported during the 4-day (Days 0-3) post-vaccination period following each dose and overall (Total vaccinated cohort)

Group	Any symptom					General symptoms					Local symptoms				
	N	n	%	95% CI		N	n	%	95% CI		N	n	%	95% CI	
				LL	UL				LL	UL				LL	UL
dTpa group	335	264	78.8	74.0	83.1	335	134	40.0	34.7	45.5	335	250	74.6	69.6	79.2
Control group	336	279	83.0	78.6	86.9	336	151	44.9	39.5	50.4	336	264	78.6	73.8	82.8

dTpa Group = This group will consist of infants born to mothers belonging to the dTpa Group in study 116945 [DTPA (BOOSTRIX)-047]. All subjects in this group will receive *Infanrix hexa* co-administered with *Prevenar 13* according to the routine national immunisation schedule.

Control Group: This group will consist of infants born to mothers belonging to the Control group in study 116945 [DTPA (BOOSTRIX)-047]. All subjects in this group will receive *Infanrix hexa* co-administered with *Prevenar 13* according to the routine national immunisation schedule.

For each dose and overall/subject:

N= number of subjects with at least 1 administered dose

n(%) = number(percentage) of subjects presenting at least 1 type of symptom whatever the study vaccine administered

For overall/dose:

N= number of administered doses

n(%) = number(percentage) of doses followed by at least 1 type of symptom whatever the study vaccine administered

95% CI = exact 95% confidence interval, LL = Lower Limit, UL = Upper Limit

Template 18 Percentage of solicited local symptoms reported during the 4-day (Day 0-3) post-vaccination period following each dose and overall (Total vaccinated cohort)

Symptom	Type	dTpa group					Control group				
		N	n	%	LL	UL	N	n	%	LL	UL
Pain	All	330	237	71.8	66.6	76.6	329	248	75.4	70.4	79.9
	Grade 3	330	24	7.3	4.7	10.6	329	20	6.1	3.8	9.2
	Medical advice	330	0	0.0	0.0	1.1	329	0	0.0	0.0	1.1
Redness (mm)	All	330	113	34.2	29.1	39.6	329	94	28.6	23.8	33.8
	Grade 3	330	4	1.2	0.3	3.1	329	1	0.3	0.0	1.7
	Medical advice	330	0	0.0	0.0	1.1	329	0	0.0	0.0	1.1
Swelling (mm)	All	330	98	29.7	24.8	34.9	329	90	27.4	22.6	32.5
	Grade 3	330	6	1.8	0.7	3.9	329	5	1.5	0.5	3.5
	Medical advice	330	0	0.0	0.0	1.1	329	0	0.0	0.0	1.1

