dTpa Group = This group will consist of infants born to mothers belonging to the dTpa Group in study 116945 [DTPA (BOOSTRIX)-047]. All subjects in this group will receive *Infanrix hexa* co-administered with *Prevenar 13* according to the routine national immunisation schedule.

Control Group: This group will consist of infants born to mothers belonging to the Control group in study 116945 [DTPA (BOOSTRIX)-047]. All subjects in this group will receive *Infanrix hexa* co-administered with *Prevenar 13* according to the routine national immunisation schedule.

For overall/subject:

N= number of subjects with at least 1 documented dose

n(%) = number(percentage) of subjects reporting the symptom at least once

95%CI= Exact 95% confidence interval; LL = lower limit, UL = upper limit

Template 19 Percentage of solicited general symptoms reported during the 4-day (Days 0-3) post-vaccination period following each dose and overall (Total vaccinated cohort)

		dTpa group					Control group				
Symptom	Type	N	n	%	95 % CI		N	n	%	95 % CI	
					LL	UL				LL	UL
Overall/subject											
Drowsiness	All										
	Grade 2 or 3										
	Grade 3										
	Related										
	Grade 3*Related										
	Medical advice										
Irritability	All										
	Grade 2 or 3										
	Grade 3										
	Related										
	Grade 3*Related										
	Medical advice										
Loss of appetite	All										
	Grade 2 or 3										
	Grade 3										
	Related										
	Grade 3*Related										
	Medical advice										
Temperature/(Axillary) (°C)	All										
	>37.5										
	>38.0										
	>38.5										
	>39.0										
	>39.5										
	Related										
	>39*Related										
	Medical advice										

dTpa Group = This group will consist of infants born to mothers belonging to the dTpa Group in study 116945 [DTPA (BOOSTRIX)-047]. All subjects in this group will receive *Infanrix hexa* co-administered with *Prevenar 13* according to the routine national immunisation schedule.

Control Group: This group will consist of infants born to mothers belonging to the Control group in study 116945 [DTPA (BOOSTRIX)-047]. All subjects in this group will receive *Infanrix hexa* co-administered with *Prevenar 13* according to the routine national immunisation schedule. For each dose and overall/subject:

N= number of subjects with at least 1 documented dose

n(%) = number(percentage) of subjects reporting the symptom at least once

For overall/subject:

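### The Day 0-3 combined symptom tables count infants without a symptom sheet as symptom-free, while the individual solicited-symptom tables exclude them, so the combined rates lean low

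*SAP*

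**What the plan says.** SAP section 5.4.1 opens its safety analyses with a composite: the percentage of infants with a local symptom, with a general symptom, and "with any symptom (solicited or unsolicited) during the 4-day (Day 0-Day 3) solicited follow-up period will be tabulated with exact 95% CI". Grade 3, related and medical-advice versions follow.

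The missing-data rules at the end of that section treat the same four days in two ways:

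- **Individual solicited symptoms.** The analysis "will include only vaccinated subjects and doses with documented safety data (i.e., symptom screen completed"). SAP section 10.1.2.3.2 repeats that a dose without a symptom sheet is left out.
- **Combined solicited and unsolicited summaries.** "For summaries reporting both solicited and unsolicited AEs, all vaccinated subjects will be considered", and infants whose parents report nothing "will be considered as subjects without the event or the concomitant medication, respectively".

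Protocol section 10.5 (Safety/reactogenicity) carries both rules, the second beginning "For summaries reporting both solicited and unsolicited AEs, all vaccinated subjects".

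The mock-table footnotes in SAP section 12 match. Template 17 (combined symptoms) defines N as the "number of subjects with at least 1 administered dose". Template 18 (individual local symptoms) defines it as the "number of subjects with at least 1 documented dose".

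**The concern.** Counting non-reporters as event-free is ordinary practice for spontaneously reported events over a long window. It fits less well here. In the Day 0-3 composite most events are solicited, and protocol section 5.6.2.14 has parents record both solicited and unsolicited events on the diary card. When the card is lost, most of the evidence about that infant goes with it, and silence says little about whether symptoms occurred.

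The resulting error has one direction. A missing sheet adds to the denominator and usually nothing to the numerator, so the composite is pulled down, which is the non-conservative direction for reactogenicity. Unequal sheet return would also feed into the comparison of the two groups. A reader comparing Templates 17 and 18 would be comparing rates on different populations.

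No planned analysis removes this. A missing symptom sheet is not among the exclusions from the ATP safety cohort (SAP sections 4.1.3 and 4.2.2), so the complementary ATP analysis would keep the same infants as symptom-free. Section 5.4 plans no composite restricted to returned sheets.

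**Working it through.** **Inputs.** All counts are from the mock tables in SAP section 12. The SAP says that its templates were taken from other recent studies and are for illustration, so they show how the denominators work and are not results of this trial.

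- Template 16, sheets returned: dTpa 330 of 335 doses, Control 329 of 336.
- Template 17, any / general / local symptoms: dTpa 264 / 134 / 250 of 335; Control 279 / 151 / 264 of 336.
- Template 18, pain: dTpa 237 of 330; Control 248 of 329.

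**Step 1: reproduce the SAP's figures.** Return is 330/335 = 98.5% and 329/336 = 97.9%. Any symptom in dTpa is 264/335 = 78.8%, with Clopper-Pearson 95% CI 74.0 to 83.1, as printed. The other five Template 17 cells also reproduce on N = 335/336, and the Template 18 pain rows reproduce on N = 330/329. The differences in N, 335 − 330 = 5 and 336 − 329 = 7, equal the unreturned sheets in Template 16. The templates therefore apply both rules.

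**Step 2: recompute the composite on returned sheets.** This assumes that every infant counted with a symptom returned a sheet.

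| Row | All vaccinated | Sheet returned | Difference (points) |
|---|---|---|---|
| dTpa, any | 264/335 = 78.8% | 264/330 = 80.0% (CI 75.3 to 84.2) | 1.2 |
| dTpa, general | 134/335 = 40.0% | 134/330 = 40.6% | 0.6 |
| dTpa, local | 250/335 = 74.6% | 250/330 = 75.8% | 1.1 |
| Control, any | 279/336 = 83.0% | 279/329 = 84.8% (CI 80.5 to 88.5) | 1.8 |
| Control, general | 151/336 = 44.9% | 151/329 = 45.9% | 1.0 |
| Control, local | 264/336 = 78.6% | 264/329 = 80.2% | 1.7 |

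(Differences are taken before rounding.) The group difference for any symptom, dTpa minus Control, is 78.8 − 83.0 = −4.2 points on all vaccinated infants and 80.0 − 84.8 = −4.8 points on returned sheets.

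**Step 3: dependence on non-return.** Let p be the rate among infants with a sheet, m the share without one, and r the share of those without a sheet who have an event recorded by another route. The tabulated rate is p(1 − m) + rm. With r = 0 and p = 80%:

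- m = 1.5%: 78.8%
- m = 2.1%: 78.3%
- m = 5%: 76.0%
- m = 10%: 72.0%

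The first two values of m correspond to Template 16. The last two, and p itself, are assumptions.

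**Step 4: can a composite fall below its own component?** Suppose that every infant with a local symptom had pain. The any-local row would be 237/335 = 70.7% against pain at 237/330 = 71.8% in dTpa, and 248/336 = 73.8% against 248/329 = 75.4% in Control. The order reverses unless at least 4 (dTpa) or 6 (Control) further infants have a local symptom other than pain. The mock counts contain 250 − 237 = 13 and 264 − 248 = 16 such infants, so there is no reversal in the 'All' rows: local 74.6% against pain 71.8%, and 78.6% against 75.4%.

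**The case against.** The case for leaving the plan alone has substance.

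- **The endpoint is not affected.** A reader might infer that the trial's main reactogenicity results are understated. The endpoint in protocol section 10.2 and SAP section 3.4 is the occurrence of solicited symptoms in Day 0-3. Templates 18 and 19 report it, and both already use documented doses. Only the composite is affected.
- **The convention is disclosed.** Protocol and SAP agree, each template states its N, Template 16 reports sheet return by group, and sites must pursue unreturned cards (protocol section 5.6.2.14). A reader could rescale.
- **Events can arrive without a card.** SAEs are reported separately and parents are questioned directly (protocol section 8.2.3.1). Treating the tabulated rate as the true rate multiplied by sheet return is therefore a limiting case. It needs r = 0 and missing sheets unrelated to symptoms.
- **The larger consequences rest on assumed return rates.** A reader might infer a reversal of rows or a spurious group difference of several points. At an assumed 80% rate with 97% return in one group and 92% in the other, the difference would be 80 × (0.97 − 0.92) = 4.0 points. Nothing in the documents points to such an imbalance: both groups receive the same vaccines, and the illustrative returns are 98.5% and 97.9%.
- **A strict restriction loses information.** An infant with a known Day 0-3 SAE but no sheet would drop out of the table.

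All of this limits the size of the problem or shapes the remedy, and the last point changes the fix. The inconsistency and its direction remain. Disclosing N does not make a missing diary evidence of no symptoms, and rescaling from Template 16 requires the reader to notice the discrepancy first.

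**Conclusion.** The point holds as a modest, one-directional inconsistency in how missing diaries are handled. Following the plan as written, the Day 0-3 combined rates are biased downward to the extent that missing sheets hide symptoms. At the illustrative return rates this is about 0.6 to 1.2 points in dTpa and 1.0 to 1.8 points in Control, with a shift of 0.6 points in the group difference for any symptom. Those differences are small beside the width of the exact intervals.

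The sizes assume that the mock counts are representative and that every counted infant returned a sheet; the trial's actual return is unknown. The effect grows with non-return, and a combined row falling below one of its components is arithmetically possible, though absent from the mock 'All' rows. All analyses are descriptive, so no formal test or decision rule depends on this table. The change is still worth making because it is cheap and makes the combined and individual tables comparable.

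**What to change.** Add to SAP section 5.4.2, and record in section 8, a rule confined to the Day 0-3 combined tables (any, local and general symptoms, with the grade 3, related and medical-advice versions):

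1. Report the rate among vaccinated infants with a completed symptom screen, either as the main row or beside the all-vaccinated row.
2. Show both Ns and footnote each denominator in Template 17.
3. List any Day 0-3 AE or SAE in infants without a sheet, so that no known event is lost.

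Keep all vaccinated infants for the 31-day unsolicited AE tables, the SAE tables, and the combined summary for registry posting (SAP section 5.4.2.1, Template 22). For that reason, add an exception instead of rewriting the general sentence in SAP section 5.4.1 and protocol section 10.5, which also governs the posting summary.

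The cost is one extra row or denominator and a short listing. Reported combined rates will be slightly higher. No new data are needed.

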5.4.2. Additional considerations

- The AEs/SAEs leading to withdrawal from the study will be generated as a listing instead of a table.
- The verbatim reports of unsolicited AEs will be reviewed by a physician and the signs and symptoms will be coded according to MedDRA. Every verbatim term will be matched with the appropriate Preferred Term. The percentage of subjects with unsolicited AEs occurring within 31-day (Day 0- Day 30) follow-up period after the booster dose with its exact 95% CI [Clopper, 1934] will be tabulated by group, and by preferred term.
- Subjects who report at least one SAE after the end of primary study 201330 [DTPA (BOOSTRIX)-048 PRI] and before the booster vaccination in 201334 [DTPA (BOOSTRIX)-049 BST: 048] study will be described in detail.
- The percentage of subjects with congenital anomaly reported across the three studies (047, 048 and 049) with its exact 95% CI [Clopper, 1934] will be tabulated by group, and by preferred term. The details of this analysis are detailed in section 9.
- The neurodevelopmental status of infants will be tabulated at both month 9 and 18.

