4.1.1. Total enrolled cohort

The Total enrolled cohort will include all enrolled subjects in the study.

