4.1.2. Total vaccinated cohort

The TVC will include all vaccinated subjects for whom data are available.

A safety analysis based on the TVC will include all subjects with booster vaccine administration documented.

- An immunogenicity analysis based on the TVC will include vaccinated subjects for whom data concerning immunogenicity endpoint measures are available.

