4.1.3. According-to-protocol cohort for analysis of safety

The ATP cohort for analysis of safety will include all subjects from the TVC who complied with the vaccine administration:

- who have received all vaccine doses in the primary study 201330 [DTPA (BOOSTRIX)-048 PRI].
- who have received the booster dose of study vaccines in the current study.
- for whom administration route and site of study vaccines is known and according to the protocol.
- who have not received a vaccine not specified or forbidden in the protocol.

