9.1. Data derivation

9.1.1. Congenital anomalies (CA)

Congenital anomalies (CA) are considered events of specific interest in maternal immunization programs and mostly recommended follow-up period seen in literature of infants born to mothers vaccinated during pregnancy is until 6 months of age. As per protocol, in Boostrix-047 study the follow-up period of infants after birth was two months. Hence, some CAs were not yet diagnosed and/or reported during the study Boostrix-047 and so these events have been reported in General Medical History section of infants in Boostrix-048 or in Boostrix-049 study. Given the importance of these safety data, medical coding of congenital anomalies reported in GMH section of Boostrix-048 (201330) and Boostrix-049 (201334) will be done. Since these CAs were not reported as SAEs and only the diagnosis code in verbatim was provided, the coding using the standard MedDRA query for the narrow CA will be performed.

An overview of all congenital anomalies both reported as unsolicited events and as pre-existing conditions in GMH section in these three studies will be present in Boostrix-049 study report, as this is the last study.

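### The three-study congenital-anomaly percentage (SAP 5.4.2 and 9.1.1) names no population, and every safety cohort the SAP defines is limited to infants who passed 049 entry, which bars major congenital defects

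*SAP*

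**What the plan says.** SAP 5.4.2 adds to the safety analyses "The percentage of subjects with congenital anomaly reported across the three studies (047, 048 and 049) with its exact 95% CI", tabulated by group and preferred term, with details deferred to section 9.

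Section 9.1.1 gives the reason: "Congenital anomalies (CA) are considered events of specific interest in maternal immunization programs". It notes that infants were followed for only two months after birth in 047, so some anomalies first appear in the general medical history of 048 or 049. Those entries will be MedDRA-coded, and the 049 report will carry the overview for all three studies because 049 is the last. The section covers sources and coding. It gives no analysis set, no denominator and no rule for infants who left before 049. The SAP's list of templates contains no congenital-anomaly table, and the TFL table of contents is filed elsewhere (SAP 10.2).

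For safety in general, SAP 5.4.1 states "The primary analysis will be based on the TVC". For unsolicited events by MedDRA term, "all vaccinated subjects will be considered", and subjects whose parents report nothing "will be considered as subjects without the event".

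Protocol 4.2 admits only infants of mothers vaccinated in 047 who completed their primary series in 048. Protocol 4.3 lists major congenital defects among the exclusion criteria and allows no deviations.

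**The concern.** The exposure of interest is the mother's vaccination in 047, so the natural question is how often her live-born infants have an anomaly. Fitness to enter a booster study at 9 months of age comes later and depends in part on the outcome being counted. Needing to have completed 048 adds to this if infants with anomalies are less likely to finish that study.

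This report is meant to be the overview of an outcome the SAP itself singles out. An exact confidence interval around a rate from a selected or mismatched set would give no sign of the problem.

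**Working it through.** **Step 1: who is in each defined set.**

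| Set | Defined in | Members |
|---|---|---|
| Total enrolled cohort | SAP 4.1.1 | "The Total enrolled cohort will include all enrolled subjects in the study" (049 enrollees) |
| TVC | SAP 4.1.2 | "A safety analysis based on the TVC will include all subjects with booster vaccine administration documented" |
| ATP cohort for safety | SAP 4.1.3 | "The ATP cohort for analysis of safety will include all subjects from the TVC who complied with the vaccine administration" |
| Adapted ATP cohort | SAP 4.1.5 | each study's own ATP immunogenicity cohort, for immunogenicity time points only |

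The first three lie behind the 049 entry criteria. The fourth spans the studies but does not cover safety. No defined safety set includes an infant who left after 047 or 048.

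**Step 2: inputs.** The plan states no anomaly rate, expected count or number of 047 live births, so there is no figure to reproduce. All of the following are assumed, and only the direction of the results is informative:
- M, prevalence of major anomalies at birth: 2 to 4%.
- m, prevalence of minor anomalies: 1 to 3%.
- q, share of major anomalies known by 049 entry and so barred: 0.5 to 1.0.
- r, share of the remaining infants who reach 049: 0.6 to 0.9, unrelated to anomaly status.

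The rate at birth is M + m, that is 3.0 to 7.0%.

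**Step 3: numerator and denominator both from 049.**

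Rate = (m + M(1 − q)) / (1 − Mq)

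- M = 3%, m = 1%, q = 0.8: 0.016 / 0.976 = 1.64%, against 4.0% at birth.
- Smallest ratio in the grid (M = 4%, m = 1%, q = 1): 0.01 / 0.96 = 1.04% against 5.0%, ratio 0.21.
- Largest ratio (M = 2%, m = 3%, q = 0.5): 0.04 / 0.99 = 4.04% against 5.0%, ratio 0.81.

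This rate is below M + m exactly when Mq(M + m) < Mq. That holds whenever Mq > 0 and M + m < 1, so the downward direction does not depend on the particular values.

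**Step 4: all anomalies from 047, 048 and 049 divided by a 049 set.**

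Rate = (M + m) / (r(1 − Mq))

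- M = 3%, m = 1%, q = 0.8, r = 0.9: 0.04 / 0.8784 = 4.55%. With r = 0.6: 0.04 / 0.5856 = 6.83%. The rate at birth is 4.0%.
- The inflation factor is 1 / (r(1 − Mq)). It runs from 1 / (0.9 × 0.99) = 1.12 to 1 / (0.6 × 0.96) = 1.74.
- Across the grid the result is 3.4 to 12.2%.

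This assumes that every anomaly is found, including in infants who left. Late diagnoses missed in leavers pull the figure down, so the rate can be too high but need not be.

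**Step 5: what the interval shows.** If every infant with a given anomaly was barred, a 049 set of the planned maximum of 340 per group shows 0/340. The exact upper limit is 1 − 0.025^(1/340) = 1.08%, however many 047 infants had the anomaly.

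**The case against.** The strongest reply is that the TVC is only inferred. The default rules sit in SAP 5.4.1, the analyses planned in the protocol, while the anomaly table is an addition in 5.4.2. The rule on unsolicited events does not clearly govern anomalies taken from medical history, which 9.1.1 says were not reported as SAEs. The neurodevelopmental tables use the Total enrolled cohort, so the TVC is not universal. The wording about all anomalies across three studies also suggests a wider set, and the Adapted ATP cohort shows that the SAP can use each study's own population. All of this stands, so a reader who infers that the SAP commits to the 049 TVC goes beyond the text. It does not supply a population, however: the Total enrolled cohort is behind the same exclusion, and a single percentage across three studies still needs one stated denominator.

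A reader might also infer that the rate must be too low. That follows only if the numerator is limited to 049 as well; step 4 shows the opposite direction.

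Nor can one say that a recognised major defect could never be counted. SAP 4.2.1 removes subjects from the TVC only for codes 1030 and 900, and eligibility violations (code 2010) affect only the immunogenicity cohort, so an infant enrolled in error would stay in. The documents do not define which defects are major, and minor or later-recognised anomalies remain. Section 9.1.1 itself expects anomalies in the 049 medical history.

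Finally, the analysis is descriptive, is not a protocol endpoint, and feeds no test or decision rule. That limits the consequence but does not remove it.

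**Conclusion.** The concern holds as a missing population with real consequences. Every safety cohort the SAP defines gives either a rate selected on its own outcome or, if all anomalies are put over a 049 set, a ratio whose parts do not match. The direction depends on which reading is programmed.

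The size cannot be derived. The ratios of 0.21 to 0.81 and 1.12 to 1.74 rest wholly on assumed prevalences, exclusion shares and retention. The conclusion also rests on the SAP text alone: the TFL table of contents may name a cohort, and the 047 and 048 protocols are not available. What is at risk is a misleading descriptive safety figure, not any inferential result.

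**What to change.** State in SAP 5.4.2 and 9.1.1 that:

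- the denominator is all live-born infants of mothers vaccinated in 116945, by maternal group;
- the numerator comes from the same infants, each counted once if an anomaly is recorded in any of the three studies, as an AE/SAE or in the general medical history;
- the numbers of infants who entered 048 and 049 are reported by group;
- anomalies reported in the two-month 047 follow-up are shown separately from those first recorded in 048 or 049, the latter over infants who entered 048.

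The split is needed because, if non-report is read as no event, infants who left early would count as free of late-diagnosed anomalies. A 049 TVC version is optional.

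The cost is SAP wording and a little more data merging. Section 9.1.1 already draws on all three studies, and Protocol 5.2.1 keeps the mother's and the infant's earlier subject numbers, so linkage exists.

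One limitation remains: late-diagnosed anomalies stay under-ascertained in infants who did not continue. The relative shortfall is loss × late-diagnosed share. For an assumed 10 to 40% loss and an assumed 10 to 50% late share, it runs from 0.1 × 0.1 = 1% to 0.4 × 0.5 = 20%. The split makes this visible but does not remove it.
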